#### **Aim 2: Week 6 to Week 12**

a) To determine the long-term efficacy of pramipexole on neurocognitive functioning in stable BD patients. b) To determine the long-term safety of pramipexole on neurocognitive functioning in stable BD patients.

**Exploratory Aim:** To integrate results from multiple dopamine-based domains (cognition; affect; reward processing) to evaluate the main and interactive effects of pramipexole on these factors in stable BD patients.

|   |   |   |
|---|---|---|
|  | Protocol Title:                           | 1/2-Prampipexole in Bipolar Disorder: Targeting Cognition (PRAM-BD) |
|   | Principal Investigator Name/Contact Info: | [name]  |
|   | Primary Contact Name/Contact Info:        | [name]
[contact]                           |
|   | Date Revised:                             | March 23, 2016 – date of IRB approval May 6, 2017                   |
|   | Study Number:                             | GCO 13-0237, HS 14-00328  |

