**Primary hypothesis testing:** 100 participants will be randomized in a 1:1 allocation to treatment with pramipexole or placebo. The primary assessment of safety will be based on the incident of adverse event rates and standardized mood ratings at each visit. Differences in the incidence of individual adverse events will be compared between randomization arms using Poisson regression. Exact 95% confidence intervals (based on the Poisson distribution) for the risk ratios for individual adverse events for treatment with pramipexole versus placebo will be computed and may incorporate an estimated overdispersion parameter if observed variability exceeds that determined by the Poisson distribution. Performance on the IGT will also be used to track potential changes in impulse-control (baseline, weeks 6 and 12). We will test for correlations between IGT performance and mania symptoms at the times of testing (simultaneous measurements). Moreover, we will use IGT change scores as predictors in regression models to evaluate changes in mania ratings at concurrent time points as well as future time points. This will directly address the question of whether or not changes in IGT strategy serve as markers of current mania and/or impending affective destabilization.

The relative specificity of pramipexole in binding to D2/D3 receptors allows for a unique opportunity to enhance DA in neural networks associated with specific aspects of cognition as well a reward processing, which will be carefully assayed in this study so that exploratory analyses will be able to test questions related to the role for these receptors across several interacting domains in BD, at least at the level of behavior. Exploratory analyses will include specific domains and individual tasks which will be modeled to account for main effects and interactions (as described in primary analyses below).

The primary outcome for efficacy is change in cognition from baseline to week 6 (MCCB Composite). The null hypothesis is that there is no difference in this change between

|   |   |  |
|---|---|--|
|  | Protocol Title:                           | 1/2-Pramipexole in Bipolar Disorder: Targeting Cognition (PRAM-BD) |
|   | Principal Investigator Name/Contact Info: | [name]   |
|   | Primary Contact Name/Contact Info:        | [name]
[contact]                          |
|   | Date Revised:                             | March 23, 2016 – date of IRB approval May 6, 2017                  |

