|   | Study Number:                             | GCO 13-0237, HS 14-00328   |

patients on pramipexole vs. patients on placebo. This will be tested in an intent-to-treat analysis using a 0.05 level two-tailed test based on a mixed effects regression model, with patients considered to be a random effect, and randomization group a fixed effect. In order to preserve statistical power, change in MCCB Composite will be used as the dependent variable; however, secondary analyses will be conducted for MCCB domain scores and measure of reward processing. The use of two post baseline evaluations (weeks 6 and 12) and the ability of the model to incorporate all available data, also improves efficiency (i.e., power). This approach will also be employed in subsequent comparisons of specific domains and for measures of reward processing. These additional analyses will be conducted at a nominal 0.05 level and will focus on enhancing interpretation of the primary analysis by highlighting the specific domains most affected by pramipexole. Since randomization is stratified by concomitant antipsychotic use and baseline depression status, indicators of stratification will be included in the model as fixed effects.

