*Missing data:* Although the mixed effects modeling approach allows patients with evaluations at week 4 but missing at week 8 to be included, bias may be introduced if missing data are related to patient response. For example, it may be that patients responding poorly are less likely to have a week 8 evaluation than those patients with better response. The mixed effects analysis would weigh the results of these poorly performing patients less (as they provide fewer data) and in the presence of a positive effect of pramipexole, decrease power. To assess the extent that any bias has been introduced by missing data, we will impute missing week 8 values. Note that if no bias is produced by the missing data, analyses with and without imputation should provide virtually identical results. If the analyses produce different results, we will work to identify the causes by comparing patients with and without missing data. Based on our prior trial experience we expect relatively few patients (< 10) to be missing the week-8 visit due to attrition. Patients with missing data will have their 8 week MCCB score imputed via multiple imputation assuming that the data are MAR, i.e., the missing nature of the variable is independent of the value of the variable given the observed data. The specific imputation model to be used will be determined prior to examination of any outcome data, but will include MCCB score at baseline and at 4 weeks. Separate imputations will be done for each randomization group.

*Due to the 12 week course of the study, mixed models will still be utilized for variables collected with sufficient frequency; however, when incorporating missing data, we will only be able to do so when at least two time points are included. Subjects with only baseline data will be included in descriptive analyses but will be dropped for analyses where necessary.*

|   |   |  |
|---|---|--|
|  | Protocol Title:                           | 1/2-Pramipexole in Bipolar Disorder: Targeting Cognition (PRAM-BD) |
|   | Principal Investigator Name/Contact Info: | [name]   |
|   | Primary Contact Name/Contact Info         | [name]
[contact]                          |
|   | Date Revised:                             | March 23, 2016 – date of IRB approval May 6, 2017                  |
|   | Study Number:                             | GCO 13-0237, HS 14-00328   |

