**Sample size/Power:** A total of one hundred patients will be randomized 1:1 (50 from ISMMS, 50 from ZHH). The adequacy of this sample size is based on the ability to reject the null hypotheses of no difference between treatment groups with respect to the MCCB composite score with sufficient power (80%). Ideally, sample size would be determined to ensure adequate power to detect the minimal clinically important difference. No specific guidelines exist to establish such a threshold in this setting but cognitive change of at least a moderate effect would likely be necessary to allow for clinical meaningfulness. Our sample size provides approximately 80% power to detect a standardized difference (e.g., Cohen’s d) of approximately 0.55 with a two-tailed 0.05 level test. For the pre-specified subgroup analysis based on concomitant use at baseline, the detectable standardized difference is about 0.80.

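### The primary null is the week 6 MCCB Composite change, but the stated mixed model pools weeks 6 and 12 and names no visit term, group-by-visit term or week 6 contrast

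*Combined protocol and SAP*

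**What the plan says.** All of this is in section 5(h) of the combined protocol and SAP, under Statistical Methods.

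- **Outcome and null.** Primary hypothesis testing states: "The primary outcome for efficacy is change in cognition from baseline to week 6 (MCCB Composite"). The null is no difference between arms in that change, tested two-sided at 0.05 by intention to treat.
- **Model.** The test comes from a "mixed effects regression model, with patients considered to be a random effect, and randomization group a fixed effect". The dependent variable is change in MCCB Composite. Because randomization is stratified by antipsychotic use and baseline depression, "indicators of stratification will be included in the model as fixed effects". No other fixed effect is named.
- **Visits used.** The same paragraph credits a gain in power to "The use of two post baseline evaluations (weeks 6 and 12) and the ability of the model to incorporate all available data".
- **Interactions.** The only mention is for the exploratory analyses, which are to account for "main effects and interactions (as described in primary analyses below"). The primary analysis text that follows describes no interaction.
- **Power.** Sample size/Power rests on the ability to "reject the null hypotheses of no difference between treatment groups with respect to the MCCB composite score", with about 80% power at a standardized difference of about 0.55. It names no visit.

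**The concern.** The declared hypothesis is about one visit and the stated model uses two. A mixed model of change at weeks 6 and 12 with group as its only treatment term has a single treatment coefficient, shared by both visits. That coefficient need not be the week 6 effect. Adding a visit main effect alone would not alter this with complete data: it absorbs the average shift between visits, such as practice, and leaves the group term common to both.

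At stake is which effect the primary p-value refers to. An analyst could defend either a pooled group term or a week 6 contrast from this text, and the two can give different answers. That choice should not stay open until the data are unblinded.

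**Working it through.** **Inputs from the documents.** 100 patients randomized 1:1, so 50 per arm; d about 0.55; two-sided 0.05; MCCB at baseline, week 6 and week 12.

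**Assumptions not in the documents.** Complete data, equal SDs of change at both visits, correlation r between the two changes (shown for 0.3, 0.6 and 0.9), and the week 12 effect. The results illustrate the issue and are not predictions.

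**Step 1: the plan's own figure.** A two-sample t test with 50 per arm at d=0.55 has noncentrality 0.55 × √(50/2) = 2.75 on 98 df. Power is 77.7% (78.5% by the normal approximation). This agrees with the stated figure of about 80% as a single comparison with no credit for a second visit.

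**Step 2: what the group coefficient estimates.** With a random patient effect, a common group term and complete data, the coefficient is the arm difference in each patient's mean of the two changes. The weights on weeks 6 and 12 are 0.50 and 0.50. If a fraction m lack week 12, the week 6 weight is

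[(1−m)/(1+r) + m] / [2(1−m)/(1+r) + m].

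At m=0.10 this is 0.53 to 0.55 for r from 0.3 to 0.9. The coefficient therefore remains close to the average.

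**Step 3: power of the pooled test.** The pooled effect is (d6+d12)/2 and the SD of the patient mean is √((1+r)/2), which is 0.806, 0.894 and 0.975 for the three values of r. The standardized pooled effect is the first divided by the second. For example, with d6=0.55, d12=0.40 and r=0.6 it is 0.475/0.894 = 0.531, giving 74.8%.

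| Effect at week 6 / week 12 | r=0.3 | r=0.6 | r=0.9 |
|---|---|---|---|
| 0.55 / 0.55 | 92.2% | 86.1% | 79.8% |
| 0.55 / 0.45 | 86.7% | 79.0% | 71.9% |
| 0.55 / 0.40 | 83.1% | 74.8% | 67.5% |
| 0.55 / 0.30 | 74.2% | 65.3% | 57.9% |
| 0 / 0.55 | 39.3% | 33.1% | 28.7% |

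The week 6 test has 77.7% in each of the first four rows and 5% in the last. In the last row the declared null is true, so the entries are rates of false rejection of that null.

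**Step 4: break-even.** Pooling loses power against a week 6 test when d12/d6 is below 2√((1+r)/2) − 1, which is 0.61, 0.79 and 0.95 for r=0.3, 0.6 and 0.9.

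**Step 5: the efficiency sentence.** With group-by-visit in the model and complete week 6 data, week 12 adds nothing to the week 6 contrast. If a fraction f lack week 6 but have week 12, the variance factor is v − r²(v−1) with v = 1/(1−f), against v without the week 12 data. At f=0.05, power rises from 75.6% to 75.8-77.3% for r from 0.3 to 0.9. At f=0.10 it rises from about 73% to about 74-77%.

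**Check by simulation** (100 trials per scenario, r=0.5, complete data). With true effects of 0.55 and 0, the group-only model averaged 0.273 and the week 6 contrast from a group-by-visit model averaged 0.556. With true effects of 0 and 0.55, the averages were 0.288 and 0.003, and the week 6 contrast rejected in 5% of trials.

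**The case against.** The strongest reply is that the text is a prose summary and does not say its list of terms is complete. It declares a week 6 null and then says that this null will be tested, so a visit-specific model may well have been intended. The power figure fits that reading, since it matches a single comparison. This stands in part: one can be confident that the terms are missing, but not that the sponsor will report a pooled coefficient. It does not close the gap, because the terms that are named do not isolate week 6.

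Second, nothing in the documents predicts that the effect fades. Section 5(f) titrates up to week 6 and then aims to hold the dose, and at r=0.6 a week 12 effect of 0.45 to 0.55 gives 79-86% against 78%. That also stands. The mismatch matters only if the effects differ, in either direction.

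Third, the efficiency sentence also credits the use of all available data, and Step 5 shows a small gain when week 6 values are missing. So it needs qualifying, not deleting.

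A reader might also take the Missing data paragraph as proof of pooling, because it says of poor responders without the later visit: "The mixed effects analysis would weigh the results of these poorly performing patients less (as they provide fewer data"). It does not discriminate. Its visits, weeks 4 and 8, match no MCCB visit, and a contrast at the second visit would down-weight those patients too.

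**Conclusion.** The concern holds as a mismatch between the declared null and the stated model, and should be fixed. Fitted as stated, the primary coefficient is about the two-visit average. The size of the consequence depends on r and on the week 12 effect, neither of which the documents give. It ranges from a gain in power with equal effects, through a loss of up to about 20 points at a week 12 effect of 0.30 (77.7% against 57.9% at r=0.9), to frequent rejection of a true week 6 null if the effect appears only at week 12.

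Three stronger readings are not supported. The documents do not show that the wrong effect will be tested, because a visit-specific model remains possible. Type I error is not inflated in general: with no effect at either visit the pooled test keeps its 5%. The sample-size statement is not in error, since it reproduces as a single comparison.

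**What to change.** In Primary hypothesis testing, add visit (6, 12) and group-by-visit to group and the stratification indicators, and name the week 6 group contrast as the single primary test at 0.05. If the two-visit average is what is wanted, restate the primary outcome and null to say so before unblinding. Qualify the efficiency sentence: for a week 6 contrast, the second visit helps only slightly, and only when some week 6 values are missing.

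Optional wording while the paragraph is open: state the within-patient covariance (a random patient effect already implies one), and say which contrast from the same model serves the efficacy part of "Aim 2: Week 6 to Week 12".

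The cost is a few lines and no new data. The downside is that if the two effects are truly equal, the week 6 contrast has less power than pooling (78% against 80-92%, depending on r), but it tests the hypothesis that the protocol states.

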bearing potential who are not using a medically accepted means of contraception (including oral contraceptive or implant, condom, diaphragm, spermicide, intrauterine device, tubal ligation, or partner with vasectomy) **10.** Women who are breastfeeding. **11.** Participation in any other investigational cognitive enhancement study within 30 days.

**Concomitant Medications:** Practical and ethical considerations prevent a focus on medication-free patients. Medications with known adverse cognitive effects will be disallowed (i.e., topiramate, anticholinergics), as will agents that may enhance cognition (e.g., amphetamine, other DA agonists). Benzodiazepines will not be allowed within 6 hours of testing. ECT in the past 12 months will be disallowed, as will any drug known to interact with pramipexole. With regard to antipsychotic medications specifically, only half of the sample will be allowed to be taking any antipsychotics. Recruitment efforts will be adjusted to ensure 50% of the sample is antipsychotic-free at baseline. Further, we will exclude any subject who is taking more than 4 concomitant psychotropic medications. Older generation neuroleptics will be specifically disallowed due to their high binding potential at the D2 receptor (Kapur et al. 1999). Although some of the standard treatments for BD (e.g. lithium) may influence cognition, it is impractical to exclude these medications given their widespread use; therefore, data will be coded for medication classes and dosages to determine a load score (as per Hassel et al. 2008) to be included as a covariate in statistical analyses.

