### Safety Outcome Measures

- Side Effects Checklist (SEC; physician administered) – (*all visits*)
- Columbia Suicide Severity Rating Scale – (*all visits*)
- Iowa Gambling Task – (*baseline, week 6, week 12*)
- Vital signs including blood pressure (standing/supine) – (*all visits*)
- Electrocardiogram (ECG) – (*screening, week 6, week 12*)
- Liver function tests; chemistry panel; CBC; urinalysis – (*screening, week 12*)
- Pregnancy test for women of childbearing age – (*screening, week 12*)
- Urine toxicology – (*screening, week 12*)
- Medication log of current medications and all medications administered during previous week – (*all visits*)

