Data from this study may be used in medical publications or presentations. The information will be de-identified so that individual subjects cannot be recognized and the information will no longer be considered PHI. The information that is collected for research will be analyzed for many years and it is not possible to know how long this

|   |   |  |
|---|---|--|
|  | Protocol Title:                           | 1/2-Pramipexole in Bipolar Disorder: Targeting Cognition (PRAM-BD) |
|   | Principal Investigator Name/Contact Info: | [name]   |
|   | Primary Contact Name/Contact Info:        | [name]
[contact]                          |
|   | Date Revised:                             | March 23, 2016 – date of IRB approval May 6, 2017                  |
|   | Study Number:                             | GCO 13-0237, HS 14-00328   |

analysis and follow-up will take. Therefore, participants are allowing access to this information indefinitely.

Participants will only be identified with a numerical code in compliance with HIPAA regulations. Raw subject data will be secured in double locked physical control. Digitized raw data will be similarly de-identified using coding and will be secured on an MS SQL server with Windows-integrated security.

**Statistical Methods: Preliminary analyses:** Groups will be compared on demographics, baseline symptom ratings, and concomitant medication load; if necessary, covariates will be included in subsequent models. MCCB data are standardized using the MCCB program, scores are age- and sex- corrected and reported on a t-score scale (Mean=50, SD=10). Any study focusing on improving cognition must consider practice effects (Goldberg et al. 2008). The placebo arm will provide estimates of expected practice so that we are able to calculate a reliable change index (RCI) to determine the meaningfulness of change (Goldberg et al. 2009).

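### The primary change-score model leaves out baseline MCCB Composite, a nearly free gain in precision; secondarily, two sections give different rules for the medication load covariate

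*Combined protocol and SAP*

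**What the plan says.** **Primary model.** Section 5(h), Primary hypothesis testing, names change in MCCB Composite from baseline to week 6 as the efficacy outcome. It is tested two-sided at 0.05 in a mixed effects regression. For that model, "change in MCCB Composite will be used as the dependent variable", patient is a random effect, group is a fixed effect, and "indicators of stratification will be included in the model as fixed effects". The indicators are antipsychotic use and baseline depression status. Both post-baseline visits, weeks 6 and 12, contribute.

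**Baseline MCCB.** Section 5(e) schedules the battery at baseline, week 6 and week 12. The Missing data paragraph puts baseline MCCB in the imputation model. No section puts it in the primary model.

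**Medication load.** The Concomitant Medications paragraph of section 5(b) says that the load score is "to be included as a covariate in statistical analyses", without a condition and without naming a visit. Section 5(h), Preliminary analyses, says: "Groups will be compared on demographics, baseline symptom ratings, and concomitant medication load; if necessary, covariates will be included in subsequent models". The primary model description does not mention load. The Safety Outcome Measures list has "Medication log of current medications and all medications administered during previous week" at all visits, so several load values per patient could be formed.

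**The concern.** A change score subtracts the whole baseline value. With equal SDs at the two visits, the best predictor of the later score subtracts only r times the baseline. A change score therefore carries avoidable noise whenever r is below 1. Entering baseline as a covariate lets the data choose the weight. Leaving it out means a wider interval for the treatment difference than the collected data allow.

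It also leaves chance baseline imbalance in the estimate. With equal SDs, an imbalance shifts the change-score difference by (1 − r) times its size, in the opposite direction. With an SD of 10 T-points, one standard error of imbalance is 10 × √(2/50) = 2 points, a shift of 0.6 points at r = 0.7. This averages to zero over randomizations but is present in the one trial that is run.

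The load question is one of pre-specification. An unconditional covariate and a covariate added only after comparing arms, with no criterion given, are different models. Two analysts following the text could fit different primary models and occasionally disagree on significance. The same conditional clause covers demographics and baseline symptom ratings.

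**Working it through.** **Inputs from the documents.** 100 patients, 1:1, so 50 per arm; two-sided alpha 0.05; standardized difference d about 0.55; power about 80% (Sample size/Power); normative T-score SD of 10 (Preliminary analyses).

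**Assumed, because the documents are silent.** Correlation r = 0.6, 0.7, 0.8, 0.9; equal SDs at the two visits unless stated; an SD of 10 in this sample; d in change-SD units unless stated.

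**1. The plan's own figure.** The noncentrality is 0.55 × √(50/2) = 2.75. Normal approximation: Φ(2.75 − 1.96) = 78.5%. Noncentral t: 77.7%. The difference detectable with 80% power is 0.560 (normal) or 0.566 (t). The stated figure is reproduced.

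**2. Variance with and without baseline, week-6 contrast.** The change score has variance 2σ²(1 − r). After adjustment for baseline it is σ²(1 − r²). The ratio is (1 − r²)/[2(1 − r)] = (1 + r)/2. The residual degrees of freedom go from 96 to 95, and estimating the extra slope multiplies the variance by (1 + 1/94). The half-width is t × 10 × √(2(1 − r)) × √(2/50) as planned, and t × 10 × √(1 − r²) × √(2/50) × √(1 + 1/94) with baseline.

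| r | Variance ratio | 95% CI half-width, T-points | CI narrower by | Power, d in change-SD units | Power, d in score-SD units |
|---|---|---|---|---|---|
| 0.6 | 0.80 | 3.55 → 3.19 | 10% | 77.7% → 85.7% | 86.1% → 92.3% |
| 0.7 | 0.85 | 3.08 → 2.85 | 7% | 77.7% → 83.6% | 94.0% → 96.7% |
| 0.8 | 0.90 | 2.51 → 2.39 | 5% | 77.7% → 81.4% | 99.1% → 99.5% |
| 0.9 | 0.95 | 1.78 → 1.74 | 2% | 77.7% → 79.3% | 100% → 100% |

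The last column uses 0.55/√(2(1 − r)) as planned and 0.55/√(1 − r²) adjusted. Its gains are 6.2, 2.7, 0.4 and 0.0 points. The plan does not say which SD standardizes d.

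If load is also added and explains nothing (94 degrees of freedom, variance × (1 + 2/93)), the change-SD powers are 85.3%, 83.2%, 81.0% and 78.9%.

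**3. If the group effect pools weeks 6 and 12.** Assume a constant effect and a correlation c between the two changes. The planned variance is multiplied by (1 + c)/2, and adding baseline multiplies it further by 1 − (1 − r)/(1 + c).
- c = 0.5 (assumed): 88.2% as planned, rising to 95.5%, 93.8%, 91.9%, 89.9%.
- c = 0.7 (assumed): 84.0% as planned, rising to 91.9%, 89.9%, 87.8%, 85.7%.

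**4. Where the gain disappears.** Let k be the baseline SD divided by the week-6 SD. The ratio becomes (1 − r²)/(1 + k² − 2rk). At k = 0.9, possible because entry requires a low screening score, it is 0.88, 0.93, 0.97 and 1.00. At r = 0.9 only the cost of the extra terms remains: 77.7% falls to 77.3% with baseline alone (0.4 points) and to 76.8% with baseline plus an uninformative load score (0.9 points).

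**5. The load rule.** 40,000 simulated trials per scenario, N = 100, group and two strata in the model, d = 0.55. Load is independent of the strata and is assumed to explain 2%, 5% or 10% of the change variance. For the conditional rule, the assumed trigger is p < 0.05 for a between-arm difference in load.
- Load always against load never: different significance verdicts in 3.6%, 5.5%, 8.0% of trials.
- Load always against the conditional rule: 3.1%, 4.7%, 7.0%.
- Type I error under the conditional rule: 0.0489, 0.0498, 0.0467 (Monte Carlo SE about 0.0011), so no inflation.
- Reference: with load explaining nothing, a separate run of 15,000 trials gave about 2.2% disagreement between always and never.

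**The case against.** **This is an optimization, not an error.** That stands. A change-score mixed model with stratification indicators is a legitimate choice and the stated power is met. A reader might infer that the trial is biased or underpowered; neither follows. If the two visits are pooled, planned power is already 84% to 88% under the assumed correlations between the two changes.

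**The gain rests on unstated quantities.** Also true. It depends on r, the SD ratio and the units of d, and runs from about 8 power points to a loss below one. What survives is the asymmetry: the losses found are under one point, and the possible gain is several times larger.

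**The plan's wording on power.** The plan gives preserving power as its reason for making change in the composite the dependent variable. That may mean using one composite instead of many domain scores. On either reading it is no argument for omitting baseline.

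**The load conflict is narrower than it looks.** A reader might infer that three places contradict one another. They do not: sections 5(b) and 5(h) Preliminary analyses conflict, while the primary model description is silent on load and does not exclude it. A reader might also infer that covariates chosen after comparing arms inflate type I error; the simulation shows no such inflation for the assumed trigger. Choosing the smaller p-value afterwards would give 0.057 to 0.063, but nothing in the plan proposes that. Much of the 3.6% disagreement at the low end is what any irrelevant covariate would produce. Stable regimens, the limit on concomitant psychotropics and the antipsychotic stratum may leave load little to explain.

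**Conclusion.** The point holds as a recommended improvement. It is not a validity problem. Omitting baseline MCCB leaves the week-6 confidence interval 2% to 10% wider than needed, measured against the planned interval, for assumed r of 0.9 down to 0.6 with equal SDs. The power gain is 1.6 to 8.0 points if d is in change-SD units and 0.0 to 6.2 points if it is in score-SD units. At high r with a smaller baseline SD it can vanish or become a loss of 0.4 points, or 0.9 points with an uninformative load score as well. The existence of a gain at equal SDs does not depend on the choice of r below 1, apart from the degree of freedom; its size does.

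The medication load point is secondary and depends on no assumed correlation. Two sections state different rules, so the covariate set of the primary model is not uniquely defined in advance. The consequence is an ambiguous primary result in a small share of trials, without inflated type I error under the conditional rule as simulated. Because no medication changes are planned during the study, the unnamed visit is mainly a gap in wording.

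**What to change.** 1. In section 5(h), Primary hypothesis testing, add baseline MCCB Composite as a fixed covariate. In the model for each secondary outcome, add that outcome's own baseline value.
2. In Preliminary analyses, replace the whole conditional-covariate clause with a statement that the between-arm comparisons are descriptive and do not determine model covariates. Deleting only the condition would leave an unconditional, unnamed covariate clause.
3. State one rule for medication load, consistent with section 5(b): the load score enters the model, taken at the baseline visit. Section 5(b) names no visit, so this has to be written in.
4. List the complete covariate set in the primary model description, and fix it before allocation is revealed.

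The cost is SAP wording and one or two residual degrees of freedom (96 to 95 or 94 for the week-6 contrast). It needs no new data, visits or patients.
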